5.3.3 Study Visits

Initial Phone Call Screening: 15 minutes

Obtain the following information and data:

- MRRC MRI safety questionnaire
- Medical history questionnaire

Screening via Zoom: 45 Minutes

Obtain the following information and data:

- Electronically signed informed consent
- Demographic data (age, sex, ethnicity, level of education, etc.)
- MoCA test
- PD Cognitive Functional Rating Scale

Online Surveys: self-paced, total of 30 min

- Geriatric Depression Scale
- Parkinson Anxiety Scale
- Starkstein Apathy scale
- PD Quality of Life Questionnaire-39
- Parkinson Fatigue Scale
- Scales for Outcomes in Parkinson's Disease – Sleep

There will be a total of 4 in-person visits:

Visit 1. Baseline Clinical Evaluation: 3 hours

Within two weeks after the initial screening visit.

Detailed clinical and cognitive evaluations including:

- MDS-UPDRS and Hoehn & Yahr
- Wechsler Test of Adult Reading
- RBANS test and executive function tests (Stroop, letter fluency (F-A-S), and Trail Making Test parts A and B)
- Neuro-QoL survey
- Structured cognitive interview for the PD-MI group
- Modified Six-Elements Test
- Structured cognitive interview for the experimental PD-MI group

Visit 2. Baseline Neuroimaging Experiments: 2 hours

Within two weeks after Visit 1.

- QMI Vividness of Imagery Scale
- Functional MRI scans during mental imagery tasks (x4) and video-watching tasks (x4)
- Instructions on respective training and homework assignments.

Training: Immediately after Visit 2. Mental imagery training and psychoeducation 3 times per week for 4 weeks. On non-training days during the week and in the subsequent 2-week block, subjects will complete homework.

Visit 3. 6-Week Post-Intervention Assessments: 3 hours. All subjects will return for repeat cognitive evaluations as in Visit 1, and mental imagery vividness rating and fMRI scans as in Visit 2.

Visit 4. 12-Week Post-Completion Assessments: 3 hours. All subjects will return for repeat cognitive evaluations and fMRI tasks. The same procedures as described in Visit 3 will be followed.

5.4 Statistical Method

5.4.1 Statistical Design

This is a phase 1 randomized clinical trial aiming to enroll 120 subjects with Parkinson's disease (PD) assigned in parallel to the experimental PD-MI (N=60) and active control PD-Con (N=60) groups. The units of observation are the subjects in these groups. Subjects will be enrolled continuously and randomized to two groups using the "minimization" method.¹⁰¹ After truly randomly allocating the first 10 subjects, each subsequent subject will be allocated to either group considering the factors age, gender, and disease stage. This method will allow us to minimize the imbalance between the groups in terms of demographic and clinical characteristics while at the same time preserving the randomness of group allocation.

We will use independent-sample t-tests and nonparametric Mann-Whitney U tests to compare subjects characteristics between the PD-MI and PD-Con groups.

We will use mixed ANOVA tests with interaction terms to assess the short- and longer-term changes in cognitive and imaging outcomes before and after training.

Our overall statistical approach is designed to address the outcomes of four different aims:

AIM 1: To determine the effects of mental imagery training on goal-directed everyday cognitive functioning in PD

Primary outcome: Change in Neuro-QoL version 2 Cognitive Function scores.⁹⁷

Manipulation check: Change in QMI Vividness of Imagery Scale scores.¹⁰⁰

Neuro-QoL version 2 Cognitive Function scores (Visit 1) and QMI scores (Visit 2) obtained at baseline and immediately upon conclusion of the 6-week intervention (Visit 3) will be compared between the PD-MI and PD-Con groups using a 2x2 mixed ANOVA with an interaction term (dependent variables: test scores, between-subject factor: group, within-subject factor: time with two levels, i.e., baseline and post-training, interaction: group-by-time) ($p < 0.05$, two-tailed).

Secondary outcomes: Change in composite z-scores obtained from the executive function tests.

We will calculate a composite z-score from the executive function test scores (i.e., Stroop,⁹⁴ F-A-S letter fluency,⁹⁵ and Trail Making A-B tests⁹⁶) for all subjects.

Composite executive function test z-scores obtained at baseline (Visit 1) and immediately upon conclusion of the 6-week intervention (Visit 3) will be compared between the PD-MI and PD-Con groups using a 2x2 mixed ANOVA with an interaction term (dependent variables: test scores, between-subject factor: group, within-subject factor: time with two levels, i.e., baseline and post-training, interaction: group-by-time) ($p < 0.05$, two-tailed).

Exploratory outcomes: 1) Change in RBANS scores,⁹³ 2) and change in The Modified Six-Element Test scores.⁹⁸

The RBANS and Modified Six-Element Test scores obtained at baseline (Visit 1) and immediately upon conclusion of the 6-week intervention (Visit 3) will be compared between the PD-MI and PD-Con groups using a 2x2 mixed ANOVA with an interaction term (dependent variables: test scores, between-subject factor: group, within-subject factor: time with two levels, i.e., baseline and post-training, interaction: group-by-time) ($p < 0.05$, two-tailed).

AIM 2: To determine the brain effects of mental imagery training in PD.

Primary outcome: Change in task-specific whole-brain pairwise functional connectivity.

We will generate group-level, task-specific, pairwise functional connectivity maps for the mental imagery and video-watching tasks using the CONN Toolbox.⁵³ These maps at baseline (Visit 2) and immediately upon conclusion of the 6-week intervention (Visit 3) will be compared between the PD-MI and PD-Con groups using a 2x2 mixed ANOVA with an interaction term (dependent variables: whole-brain pairwise functional connectivity maps, between-subject factor: group, within-subject factor: time with two levels, i.e., baseline and post-training,

interaction: group-by-time). We will use the false discovery rate (FDR)-correction for multiple comparisons ($p < 0.05$, two-tailed).¹⁰²

Secondary outcomes: Change in task-specific graph-based local and global network measures.

Based on the pairwise functional connectivity maps, we will compute the clustering coefficient and betweenness centrality representing local and global graph measures, respectively, using the CONN Toolbox.⁵³ These graph measures associated with the mental imagery and video-watching tasks performed at baseline (Visit 2) and immediately upon conclusion of the 6-week intervention (Visit 3) will be compared between the PD-MI and PD-Con groups using a 2x2 mixed ANOVA with an interaction term (dependent variables: graph measures, between-subject factor: group, within-subject factor: time with two levels, i.e., baseline and post-training, interaction: group-by-time). We will use the FDR-correction for multiple comparisons ($p < 0.05$, two-tailed).¹⁰²

Behavioral scanning data: We will add up the number of key elements of the recorded mental imagery descriptions for each scan (e.g., entities, sensory descriptions, spatial/temporal references, thoughts, actions, emotions, task components) and average them across scans to obtain an average imagery content score per subject. We will also average the number of correct answers to content-related questions after video-watching scans to obtain an average accuracy score per subject. The average mental imagery content and video-watching accuracy scores performed at baseline (Visit 2) and immediately upon conclusion of the 6-week intervention (Visit 3) will be compared between the two groups using a 2x2 mixed ANOVA with an interaction term (dependent variables: average scores, between-subject factor: group, within-subject factor: time with two levels, i.e., baseline and post-training, interaction: group-by-time) ($p < 0.05$, two-tailed).

AIM 3: To determine whether the cognitive and brain effects of mental imagery training in PD are sustained

The primary, secondary and exploratory outcomes as outlined in Aims 1 and 2 will also apply to Aim 3. All cognitive and functional MRI tasks will be repeated 12 weeks after the completion of the training program (Visit 4). These results will then be compared with those obtained at baseline and 6-week post-intervention using a 3x2 mixed ANOVA with an interaction term (dependent variables: cognitive test scores and functional connectivity and graph measures, between-subject factor: group, within-subject factor: time with three levels, i.e., baseline, 6-weeks post-intervention, and 12-weeks post-completion, interaction: group-by-time) ($p < 0.05$, two-tailed). A significant interaction will be followed by post hoc simple effects tests to determine the level(s) of interaction.

AIM 4: To explore the brain-cognition link associated with mental imagery training in PD

Exploratory Aim: We will examine the post-training brain-cognition relationship at the 6-week and 12-week timepoints in each group. We will test whether the post-training changes in task-specific whole-brain pairwise functional connectivity and graph measurements will predict the post-training differences in the Neuro-QoL Cognitive Function and composite executive test scores in each group.

Exploratory outcomes: This brain-behavior relationship at 6 weeks will be the exploratory outcome of Aim 2 and that at 12 weeks will be the exploratory outcome of Aim 3.

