5.4.2 Sample Size Considerations

We calculated the sample size based on the primary cognitive outcome, i.e., Neuro-QoL version 2 Cognitive Function scores. The Neuro-QoL Cognitive Function validation study with 120 PD patients who had mild disease (Hoehn & Yahr stage 2) showed mean \pm SD = 50.46 \pm

7.25.⁹⁷ A change of 2-6 T-scores have been considered a minimally important change in patient-reported outcome measures.¹⁰³

We estimated the sample size based on the assumption that there will be an average of 4 T-score improvement after mental imagery training using the G*Power 3.1 software^{104,105}. The repeated-measures ANOVA between-subject factor model with two groups and two measurements, with an effect size of $f=0.266$ (corresponding to a moderate effect size $d=0.53$), alpha 0.05, and power 0.80 yielded a total sample size of 86 (43 in each group). With an estimated 15% drop out ($86/0.85 \approx 101$) during the 6-week intervention period and another 15% drop out ($101/0.85 \approx 120$) in the subsequent 12-week period, we plan to recruit 120 subjects in total.

In our previous work with PD patients using motor (N=22) and visual (N=22) imagery training, we showed robust task-specific pairwise functional connectivity changes post-training especially in the respective motor and visual networks.⁴ Therefore, we think this sample size will also be adequate for the primary imaging outcome.

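### The Aim 1 test of Neuro-QoL is a change-score t-test: valid, but less precise than adjusting the post-training score for the baseline score already collected

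*Combined protocol and SAP*

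**What the plan says.** Section 5.4.1 (Aim 1) names the outcome: "Primary outcome: Change in Neuro-QoL version 2 Cognitive Function scores". Visit 1 and Visit 3 scores "will be compared between the PD-MI and PD-Con groups using a 2x2 mixed ANOVA with an interaction term", with the group-by-time term tested two-sided at 0.05.

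The same model serves the secondary outcome: "Composite executive function test z-scores obtained at baseline (Visit 1) and immediately upon conclusion of the 6-week intervention (Visit 3) will be compared" in the same way. It also serves RBANS, the Modified Six-Elements Test and QMI. Aim 3 adds Visit 4: "These results will then be compared with those obtained at baseline and 6-week post-intervention using a 3x2 mixed ANOVA with an interaction term".

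Covariates appear in two places. Section 5.4.3 puts sex into separate models. Section 5.4.4 adds nonmotor survey scores if they differ significantly between groups. The baseline value of the outcome is not named in either. Baseline Neuro-QoL is collected at Visit 1 (Sections 5.1 and 5.1.1). The minimization factors in 5.4.1 are age, gender and disease stage, so Neuro-QoL is not balanced by design.

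Section 5.4.2 sizes the trial with a different model: "The repeated-measures ANOVA between-subject factor model with two groups and two measurements", f = 0.266 (d = 0.53), "alpha 0.05, and power 0.80 yielded a total sample size of 86 (43 in each group".

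**The concern.** A change score fixes the slope of follow-up on baseline at 1, whatever the real correlation between visits. When the true slope is lower, the analysis subtracts too much of the baseline score. This adds noise and leaves part of any chance baseline difference in the estimate. ANCOVA estimates the slope from the data.

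At stake is precision on the primary cognitive question. The loss depends on a correlation that the plan does not state. Nothing is gained in return, because the baseline score is collected anyway.

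**Working it through.** **Inputs.** From Section 5.4.2: f = 0.266, so d = 2 × 0.266 = 0.532; alpha 0.05; 43 per arm evaluable; SD 7.25; assumed improvement 4 T-score points; 15% dropout by T1. From Section 4.3.1: 60 per arm, so 60 × 0.85 = 51 per arm expected at T1. Assumptions, because the documents are silent: the correlation r between visits, and equal SDs at both visits.

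**1. The plan's own N.** The between-factor model has noncentrality λ = f²·N·m / (1 + (m − 1)r), with m = 2. At r = 0.5, λ = 0.0708 × 86 × 2 / 1.5 = 8.11 and power is 0.804, so N = 86 reproduces. The other values tried give 58 (r = 0), 76 (0.3), 98 (0.7) and 102 (0.8). The plan's N therefore points to r = 0.5.

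**2. The planned test is a change-score t-test.** In a test data set the interaction F and the squared t on T1 − T0 were both 9.5847.

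**3. Variances (equal SDs).** Per subject, the change score has 2·SD²(1 − r) and ANCOVA has SD²(1 − r²). The ratio is (1 − r²) / [2(1 − r)] = (1 + r)/2. Simulation at 43 per arm (20,000 trials) gave 0.664, 0.759 and 0.908 at r = 0.3, 0.5 and 0.8, close to the formula's 0.65, 0.75 and 0.90. Both estimators averaged about 4.0 when the true effect was 4.

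**4. Power at d = 0.532 (noncentral t, two-sided 0.05).** Each cell gives change score / ANCOVA.

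| r | Variance reduction | 43 per arm | 51 per arm |
|---|---|---|---|
| 0.3 | 35% | 54.0% / 72.4% | 61.4% / 79.6% |
| 0.5 | 25% | 68.4% / 80.4% | 75.8% / 86.7% |
| 0.6 | 20% | 77.8% / 86.2% | 84.5% / 91.4% |
| 0.7 | 15% | 88.3% / 92.7% | 93.0% / 96.1% |
| 0.8 | 10% | 97.1% / 98.2% | 98.8% / 99.3% |

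The stated 4 points over SD 7.25 give d = 4/7.25 = 0.552, slightly above the d used for sizing. At r = 0.5 power is then 71.5% / 83.1% at 43 per arm and 78.8% / 89.0% at 51 per arm.

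**5. Precision at 51 per arm, r = 0.5.**
- Change score: residual SD 7.25 × √(2 × 0.5) = 7.25; SE 7.25 × √(2/51) = 1.44; 95% CI half-width 2.85.
- ANCOVA: residual SD 7.25 × √0.75 = 6.28; SE 1.24; half-width 2.47.

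**6. Baseline imbalance.** The two estimates differ by (1 − slope) × baseline gap. A one-SE chance gap of 1.44 points at slope 0.5 moves the change-score estimate by 0.5 × 1.44 = 0.72 points relative to ANCOVA.

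**7. Unequal SDs.** With post-training SD = k × baseline SD, the reduction is 1 − (1 − r²)k² / (1 + k² − 2rk). Over r = 0.3 to 0.8 it is about 0–24% at k = 1.2 and about 36–50% at k = 0.8.

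**The case against.** The strongest reply is that the planned test is sound. It is an unbiased test of the outcome as the plan defines it, a change in score, and ANCOVA is only a more efficient choice. That stands. A reader might infer that the primary analysis is wrong or biased; the documents do not support this.

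A reader might also infer that the choice of test alone leaves the trial underpowered, at 68% instead of 80%. That goes too far, for three reasons.
- The figure uses 43 per arm, while 5.4.2 expects about 101 subjects after the 6-week dropout. At 51 per arm and r = 0.5 the planned test has 76%, or 79% on the 4-point and SD 7.25 inputs.
- The 68% also reflects a separate mismatch: 5.4.2 sizes a between-subject factor, whereas 5.4.1 tests an interaction. ANCOVA recovers 80% at 43 per arm because (1 + r)/2 equals 1 − r² at r = 0.5. At r = 0.3 it too falls short, at 72%.
- The true r is unknown. At 0.7 the planned test has 88% even with 43 per arm.

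Nor is the variance gain a fixed property of the design. A range of 10–35% needs r between 0.3 and 0.8 and equal SDs, neither of which the documents state. The two methods also share an estimand, not an estimate: in one simulated trial at r = 0.5 they differed by 0.63 points on average.

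Timing limits how far the remedy reaches. Section 4.1.1 randomises at the end of Visit 1, and QMI and fMRI baselines are taken at Visit 2, so those baselines follow allocation. For Neuro-QoL, the Visit 1 description in 5.1 mentions randomisation before the survey, which does not fit clearly with 4.1.1. A baseline taken after allocation is known would weaken a change score too, so this is a reason to settle the order and not a reason to keep the ANOVA.

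**Conclusion.** The concern holds as a free gain in efficiency. The planned test is valid but fixes the baseline slope at 1, and no outcome model adjusts for the outcome's own baseline.

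With equal SDs and r = 0.5, the correlation that reproduces the plan's N, ANCOVA has 25% less variance and raises power at 51 per arm from 76% to 87% (d = 0.532). The advantage is larger at lower r, small from r = 0.7 upward, and could be close to nil if the post-training SD is well above the baseline SD and r is high. The algebra is certain; the size of the gain rests on these assumptions. ANCOVA's guarantee of at least equal precision is a large-sample one, and it spends one degree of freedom.

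**What to change.** In Section 5.4.1:
- For Neuro-QoL, the executive composite, RBANS and the Modified Six-Elements Test, replace the 2x2 ANOVA with a linear model of the T1 score on group and the baseline score. Report the adjusted mean difference with its 95% CI.
- Where 5.4.6 triggers multiple imputation (more than 5% missing, primary cognitive outcome only), fit this model in each imputed data set and pool.
- For the Aim 3 cognitive outcomes, replace the 3x2 ANOVA with a baseline-adjusted mixed model that gives separate T1 and T2 group contrasts.
- State that baseline scores are obtained before allocation is known, and reconcile 4.1.1 with the Visit 1 description in 5.1.
- Do not extend the change to the connectivity analyses. Extend it to QMI only with the caveat that its baseline is taken at Visit 2, after randomisation.

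The cost is SAP wording, best settled before outcome data are examined. No new data, subjects or visits are needed.

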To compare the task-specific whole-brain functional connectivity changes between the groups, we will perform pairwise functional connectivity analyses using the generalized psychophysiological interaction (gPPI) model. We will first convolve the 3-min task blocks in each mental imagery and video-watching run with the canonical hemodynamic response function. We will use the functionally defined cortical and subcortical nodes (N=268) of the whole-brain Shen atlas.⁵² For each subject, we will extract the average blood oxygenation level-dependent signal time courses calculated via the gPPI model from these nodes and correlate them with each other using Pearson correlations. The r values will correspond to the functional connectivity strength between node pairs. We will Fisher z-transform the r values and obtain group-level functional connectivity maps for statistical analyses.

Graph analysis

To compare the task-specific changes in local and global network properties between the groups, we will perform graph analyses on the pairwise functional connectivity data. Specifically, we will compute the 1) clustering coefficient, which shows the connectivity strength between neighboring nodes and is a measure of local network efficiency, and 2) betweenness centrality, which shows how well-connected a particular node is with all other nodes and is a measure of that node's potential as an integrative hub.¹⁰⁶ These graph measures will then be used in statistical analyses.

Sex as a biological variable

Sex differences in normal cognitive aging have been reported.¹⁰⁷ Reports on sex differences in PD-related cognitive decline have been variable. Sex differences in cognition in de novo PD patients have been found to be similar to those in normal aging.¹⁰⁸ On the other hand, male sex was found to be associated with PD-MCI,¹⁰⁹ and poorer performance in male vs female PD patients in executive functioning and processing speed have been demonstrated.¹¹⁰ In our study, both groups will be sex-matched and we will use sex as a covariate in separate analytical models to examine the potential sex-related differences in training response.

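### Aim 3 tests connectivity and graph measures at p < 0.05 without the FDR correction that Aim 2 states for the same measures

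*Combined protocol and SAP*

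**What the plan says.** Section 5.4.1 (Statistical Design) sets the testing rules aim by aim.

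- **Aim 1**, single scores such as Neuro-QoL: 2x2 mixed ANOVA, two-tailed 0.05, no correction named.
- **Aim 2**, pairwise connectivity: 2x2 mixed ANOVA, then "We will use the false discovery rate (FDR)-correction for multiple comparisons ($p < 0.05$, two-tailed".
- **Aim 2**, graph measures: the same design, then "We will use the FDR-correction for multiple comparisons ($p < 0.05$, two-tailed".
- **Aim 3**, everything repeated at Visit 4: a newly specified 3x2 mixed ANOVA with "dependent variables: cognitive test scores and functional connectivity and graph measures". The rule given is "interaction: group-by-time) ($p < 0.05$, two-tailed). A significant interaction will be followed by post hoc simple effects tests".

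The only link from Aim 3 back to the earlier aims is "The primary, secondary and exploratory outcomes as outlined in Aims 1 and 2 will also apply to Aim 3". It names outcomes. It does not mention thresholds or corrections.

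Section 5.4.3 (Planned Analyses) fixes the scale of the connectivity analysis: "We will use the functionally defined cortical and subcortical nodes (N=268) of the whole-brain Shen atlas", with Pearson correlations between nodes. Neither that section nor 5.4.6 (Handling of Missing Data) gives a correction for Aim 3.

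Section 4.2.1 lists change in pairwise connectivity up to the 12-week follow-up among the primary imaging outcomes. It counts a significant increase in major networks as sustained improvement. Section 3.3 makes sustained effect the secondary objective.

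**The concern.** The same imaging measures are tested under two rules. In Aim 2 the 0.05 level follows a sentence that calls for FDR. In Aim 3 it stands alone and covers single cognitive scores and tens of thousands of node pairs alike. An analyst who follows Aim 3 as written would apply to whole-brain maps the rule that the plan otherwise uses for single scores.

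Two things are at stake. First, the claim of sustained reorganisation rests on significant connections in major networks. The plan names those networks only as examples, and it sets neither a specific connection nor a minimum number of connections. Uncorrected testing over a very large family produces many chance findings from which such a claim could be drawn.

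Second, the baseline and 6-week scans enter both analyses. A connection that fails FDR in Aim 2 could be significant in Aim 3 partly because the bar was lowered. An effect might then look sustained, or newly emerged, for that reason alone. Afterwards a reader could not tell which rule had been pre-specified.

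**Working it through.** **The plan's own figures.** The documents state no false-positive count. Their only calculated design figure is the sample size in 5.4.2: f = 0.266, alpha 0.05, power 0.80, total 86. The noncentral F calculation for the between-subject factor, with two groups and two measurements, returns N = 86 and power 0.804 if the correlation between measurements is 0.5. That correlation is an assumption, because the plan does not state it. The figure does not bear on the point. N = 86 is used below only to size the simulation.

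**Inputs.** 268 nodes and Pearson correlations (5.4.3), two tasks (5.4.1, Aim 2), threshold 0.05 (5.4.1, Aim 3).

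**Step 1: number of tests.** Pearson correlation is symmetric, so pairs are unordered:

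268 × 267 / 2 = 35,778 node pairs per task.

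**Step 2: expected rejections of the interaction with no correction.** If no pair has a true group-by-time effect:

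35,778 × 0.05 = 1,788.9 per task, and 2 × 1,788.9 = 3,577.8 over both tasks.

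If some pairs have true effects, the expected number of false positives is 0.05 × (number of null pairs).

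**Step 3: does correlation between pairs change this?** The expected count is a sum of individual probabilities, so dependence does not alter it; it alters the spread. As a check, null 3x2 mixed ANOVA interactions were simulated on 35,778 pairs with N = 86. In the correlated case, 20 shared factors carried half of the error variance.

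| Simulated null data | Datasets | Pairs with p < 0.05, uncorrected | Pairs significant with Benjamini-Hochberg FDR at 0.05 |
|---|---|---|---|
| Independent pairs | 5 | 1,685 to 1,860 (mean 1,770) | 0 in every dataset |
| Correlated pairs | 15 | 973 to 2,747 (mean about 1,700) | 0 in every dataset |

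The runs are few, but they agree with the arithmetic.

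**Step 4: within one network.** The documents give no node count per network. Assume 10 to 30 nodes:

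- 10 nodes: 10 × 9 / 2 = 45 pairs; 45 × 0.05 = 2.25 expected null rejections.
- 30 nodes: 30 × 29 / 2 = 435 pairs; 435 × 0.05 = 21.75 expected null rejections.

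These counts ignore direction. With 45 independent pairs, the chance of no rejection is 0.95^45, about 10%. It is higher once an increase is required.

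**Step 5: graph measures.** If each measure is tested at every node, 268 × 0.05 = 13.4 per measure per task. That is 26.8 per task for two measures and 53.6 over two tasks. The plan does not say that the group tests are run per node, so these counts are conditional.

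**The case against.** The best defence is that the omission is one of drafting. In Aim 2 the same two-tailed 0.05 follows the FDR sentence and denotes the corrected level, so those words alone need not mean uncorrected. Aim 3 compresses all cognitive and imaging analyses into one sentence and opens by referring back to Aims 1 and 2. The team's earlier connectivity results, shown in Figures 1 and 2 of section 1.2, are reported as FDR-corrected. All of this stands as evidence of intent. A reader might infer that the plan rejects FDR for Aim 3; the documents do not support that, since they are silent on the correction. Intent does not settle the rule, however. Aim 3 restates its design, variables and threshold in full, and what it carries over is outcomes.

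Three stronger readings also fail.

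- A reader might infer that every network would show significant connections and that the imaging result would always look positive. Section 4.2.1 asks for an increase in major networks, whereas 35,778 is a whole-brain count and a three-level interaction has no sign. Step 4 shows that chance findings within a network are likely, not certain.
- A reader might add further false connections from the post hoc tests. Those tests run only after a significant interaction, so they cannot add pairs to those already counted. They can only mislocate the effect within them.
- A reader might take the graph-measure counts as fixed. They hold only if testing is per node.

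**Conclusion.** The point holds. Aim 3 states a threshold for connectivity and graph measures without the FDR correction that Aim 2 gives for the same measures, and nothing elsewhere in the documents fills the gap.

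Its size is about 1,789 expected false-positive node pairs per task on the interaction test. This rests on two conditions: Aim 3 is followed literally, and no pair has a true group-by-time effect. Without the second condition, the figure is 0.05 times the number of null pairs.

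The supported consequence is that chance findings within major networks become likely and that results at the 12-week follow-up are judged more leniently than those at 6 weeks. A guaranteed positive imaging result is not shown. Because a primary imaging outcome is affected and the correction is simple, the text should be changed before Visit 4 imaging data are analysed.

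**What to change.** Add to Aim 3 in section 5.4.1: *For functional connectivity and graph measures, the FDR correction of Aim 2 applies to the 3x2 group-by-time interaction, across all node pairs (or across all nodes, if graph measures are tested per node) within each task. Post hoc simple effects tests on these measures are also corrected for multiple comparisons.*

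The text should name the method and the family of tests for the post hoc correction, and say whether graph measures are tested per node. The correction has to name the interaction, because that is the test Aim 3 specifies and the one that generates the expected false positives. The stated threshold for cognitive scores is unchanged.

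The cost is a short addition to the text and fewer connections declared significant, with some loss of sensitivity to real but weak effects. Design, sample size and data collection do not change.
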